## II. Background and Rationale

Overactive bladder (OAB) is a common condition with a prevalence ranging from 5.9% to 16.9% in the United States and has been found to increase with age. OAB has a negative impact on health related quality of life (QoL), and OAB patients have more anxiety and depression than controls. Primary treatments for OAB include behavioral modifications, such as decreased caffeine intake and timed voiding, and pelvic floor physical therapy. Second line therapy includes anticholinergic medicine/beta-3 adrenoceptor agonists. Unfortunately, compliance and adherence to these medications decreases over time likely due to side effects and/or efficacy. Per American Urological Association and the Society of Urodynamics, Female Pelvic Medicine and Urogenital Reconstruction (AUA/SUFU) guidelines, onabotulinumtoxinA (BTX) is a third line recommendation for OAB along with percutaneous tibial nerve stimulation (PTNS) and sacral neuromodulation (SNS).

The Food and Drug Administration (FDA) first gave BTX initial approval for use in 1989. BTX, however, was first described for use in the urinary bladder by Stohrer and colleagues in 1999. It was FDA approved for use in neurogenic detrusor overactivity in 2011 and refractory idiopathic detrusor overactivity or overactive bladder in 2013. Since 1999 many studies have looked at the delivery and dosage of this neurotoxin into the bladder for OAB. In the beginning, patients were receiving BTX through as many as fifty injection sites, but after many studies confirmed similar efficacy, it is now common practice to inject BTX through ten injection sites. Similarly, studies have looked at the appropriate dosage of BTX for OAB; the results of these studies have indicated 100 units(U) as the best dose for non-neurogenic patients with OAB. BTX has transitioned over the years from a procedure conducted in the operating room to one that is commonly done in the clinic or physician office. Consequently, there has been continuing interest in reducing the number of injection sites further to make the technique more tolerable and more efficient. Preclinical studies in rats have shown similar effects of BTX between four and eight injection sites. Additionally, Avallone et al recently published a pilot study which evaluated the use of one, two and three total injection sites (one for each 100 U). Their population included idiopathic detrusor overactivity (IDO) as well as neurogenic detrusor overactivity (NDO) patients. They found administering BTX via one to three sites had similar clinical efficacy and rates of adverse events compared to the established protocol for the respective groups.

Due to these findings, we propose a randomized study where refractory OAB patients receive 100 U of BTX over either 3 or 10 injection sites. We will maintain the currently accepted dilution standard for BTX as there have not been studies specifically researching this factor yet. BTX will be reconstituted at a concentration of 10 U per 1 cc; 100 U will be reconstituted with 10 cc of injectable saline.

We have chosen three sites over one injection site specifically because an MRI study completed by Mehnert et al reported, on average, 17.6% of injected BTX was found at the middle or lateral aspects outside of the bladder dome. There was, however, one patient who had contrast beyond the bladder base. Of note, this study had two arms: a 30-site group and a 10-site group with three neurogenic detrusor overactivity patients in each. The 30-site group had 300 U of BTX diluted in 27 cc of injectable saline plus 3 cc of gadopentetate (MRI contrast agent) while the 10-site group had 300 U of BTX diluted in 9 cc of injectable saline plus 1 cc of gadopentetate. Despite nearly 20% of the injected BTX being found outside of the bladder, coverage of the detrusor coverage, this was found to be sufficient enough to report similar success rates as reported in the literature. Due to the findings in this study that 20% of the injection can be found outside of the bladder, we decided against a single injection and opted for three injection sites.

OAB is a prevalent condition affecting up to one of every 6 adults. BTX is a wellestablished third line therapy for refractory OAB. Decreasing the number of injection sites may improve patient tolerability and satisfaction with this office-based procedure and potentially reduce the rates of adverse events (AEs) including hematuria and urinary tract infection (UTI).

Although a pilot study has been published regarding injection sites as few as one for 100 U of BTX, there has not been a randomized study comparing fewer injections sites to what is commonly practiced (ten injection sites). We hypothesize that a 3-site injection method is as effective as 10-site method and will lead to higher patient satisfaction.

#### III. Objectives and Endpoints

The primary aim of this study is to determine whether distributing 100 U of onabotulinumtoxinA over less injection sites (three) is just as effective as common practice (ten).

Our secondary aim is to assess whether less injection sites has fewer complications (UTI/ hematuria) and leads to better patient satisfaction and tolerability as this procedure is done in the office while the patient is awake.

We hypothesize that a 3-site injection method is as effective as a 10-site method and will lead to higher patient satisfaction. The primary outcome will be incontinence episodes per day assessed at 3 months after BTX injection. Secondary outcomes will include voiding symptom scores and voiding diary parameters as measured by the Overactive Bladder Questionnaire-Short Form (OABq-SF), International Consultation on Incontinence Questionnaire-Short Form (ICIQ-SF), Global Response Assessment (GRA), Visual Analog Scale (VAS) on the day of injection to assess for pain, satisfaction, and tolerability, and 3-day voiding diaries to be completed throughout the study.

#### IV. Methodology

Although a pilot study has been published regarding injection sites as few as one for 100 U of BTX, there has not been a randomized study comparing fewer injections sites to what is commonly practiced (ten injection sites).

Patients diagnosed with OAB and that have failed first and second line treatments will be presented with all third line therapies including BTX, SNS, and PTNS. Patients choosing BTX will be offered an opportunity to enroll in this study. If patients are already clinical responders and currently receiving BTX therapy, they are eligible for randomization if they choose to participate in the study. If they had prior BTX and were clinical non-responders they will not be eligible. Clinical non-responders are patients who previously reported no subjective improvement in their symptoms by 3 months after their injection. If a patient was an initial responder (with subjective improvement reported by the patient), and the effect has since worn off, the earliest they can receive re-injection will be 3 months after their initial injection. All repeat injections will be done at with a minimum of 3 months in between injections.

Consent to send out pre-screening activities may be done by telephone script with all elements of information sheet included. Participant agreement is consent to send prescreening activities. Once the participant is present for enrollment visit, a formal consent will be performed for study participation. Informed consent will be obtained from all patients prior to conducting any study activities. Consented patients will complete the OAB-g SF, ICIQ-SF, 3-day voiding diary and enrollment guestionnaire (demographics, medical history, concomitant medications, etc.) prior to study enrollment. A urinalysis (UA) will be collected at this visit as well and a urine culture (UCx) will be performed, if necessary. If the patient meets the eligibility criteria, they will be randomized (1:1) into the 3-injection site group or the 10injection site group. We plan on performing a stratified randomization so the number of BTX naïve and previous BTX responder patients will be equivalent in both arms in order to minimize selection bias. Patients will be blinded to the number of injections they will receive. Adverse events and concomitant medications will be assessed at each follow-up visit. A diary will also be completed, collected and reviewed at each follow-up visit. GRA will also be gathered at each follow up visit. Visual Analog Scores will be gathered at the end of the injection visit to assess for patient satisfaction, pain, and tolerability.

Patients will be asked to remain off any oral anticholinergic or beta-3 agonist medications, PTNS therapy, or any neuromodulation throughout the entirety of the study.

Patients will follow up two weeks post-injection (±7days) for an office visit. OAB-q SF, GRA, ICIQ-SF, 3-day voiding diary, UA and post void residual (PVR) will be collected. If necessary, a UCx will be ordered for evaluation.

At 3, 6, 9, and 12 months post-injection (± 14 days), patients will return for follow-up appointments. OAB-q SF, GRA, ICIQ-SF, patient satisfaction, 3-day voiding diary, and UA will be collected. If necessary, a UCx will be ordered for evaluation. We will also assess for adverse events and concomitant medications at each of these visits. Specific adverse events we will be tracking include urinary retention (inability to void), elevated PVR of greater than 300 cc, UTI, excessive bleeding at injection sites that requires cautery, and systemic BTX effects (systemic weakness). If at any visit the patient is found to have a UTI, they will be prompted to repeat that visits questionnaires and 3-day diary at an unscheduled visit once the prescribed UTI treatment has been completed. At the unscheduled visit AEs will be reviewed and a clinical decision will be made by an investigator if UTI symptoms are still present after treatment completion. The unscheduled visit will occur at the urology research clinic.

If a repeat botox injection is given at the 3, 6, or 9 month visit, the subject will have a 2 week follow up visit identical to visit 3 in the schedule of events before continuing to be followed every 3 months.

While in-person visits are preferable, if the patient is unwilling or unable to attend a study visit (specifically visits 4-7) they will not be withdrawn from the study. In order to assess patient safety and provide continuing follow-up, the patient may be contacted by phone and/or mail. If necessary, study information may be collected by either or both of these methods; phone (current medications, AE assessment) and/or mail (questionnaires, voiding diary). If a patient requires a remote visit, they may complete at least one, but not all visits remotely.

	Consent and Screening	Enrollment and Treatment	2 Weeks Post-BTX Visit (±7 days)	3 Months Post-BTX Visit d (± 14 days)	6 Months Post-BTX Visit d (± 14 days)	9 Months Post-BTX Visit d (± 14 days)	12 Months Post-BTX Visit (± 14 days)
	Visit 1	Visit 2	Visit 3	Visit 4	Visit 5	Visit 6	Visit 7
Consent	X						
Eligibility	X						
Demographics, Medical History	X						
OABq-SF ICIQ-SF	X		X	X	X	X	X
3-day Voiding Diary	X		X	X	X	X	X
Urinalysis, Urine Culture as needed	X	X	X	X	X	X	X
Pregnancy test before injection as needed a	X	X		X	X	X	
Post void residual (PVR) ♭			Х				
BTX injection		X					
Repeat BTX				X	X	X	

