#### VII. Data Analysis

**Statistical Analysis** 

#### Primary Effectiveness

The primary efficacy endpoint is defined as at least a 50% reduction in number of urgency related incontinence episodes at 3 months. The number of urgency incontinent episodes per day is measured as the average of two, 3-day, consecutive bladder diaries. Patients shall be classified as treatment successes or treatment failures based on this criterion.

The primary hypothesis is that the proportion of patients who are treatment successes with BTX-3 is non-inferior with a margin of 15% to that with BTX-10 at 3 months.

 $H_{o}: p_{BTX-3} \le p_{BTX-10} - 0.15 \text{ vs}$   $H_{a}: p_{BTX-3} > p_{BTX-10} - 0.15$ 

In the hypothesis equations, 0.15 is the clinical equivalence margin for the non-inferiority test of this hypothesis.

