#### Sample Size and Power Calculation

One hundred seventy-eight (178 patients will be randomized in this study, 89 per group to achieve 80% power to detect a non-inferiority margin difference between the group proportions of 0.15. The reference group (BTX-10) proportion is 0.85. The treatment group proportion (BTX-3) is assumed to be larger than 0.70 under the null hypothesis of inferiority. The power was computed for the case when the actual treatment group proportion is 0.85, that is both BTX-10 and BTX-3 had the same response rate of 0.85. The test statistic used is the one-sided Z test with a Type I error rate of 0.025.

Power	N1	N2	N	Reference (BTX-10) Responder Rate	BTX-3 Responder RatejH0	BTX-3 Responder Rate Ha
0.8	147	147	294	0.7	0.55	0.7
0.85	168	168	336	0.7	0.55	0.7
0.9	197	197	394	0.7	0.55	0.7
0.8	131	131	262	0.75	0.6	0.75
0.85	150	150	300	0.75	0.6	0.75
0.9	176	176	352	0.75	0.6	0.75
0.8	112	112	224	0.8	0.65	0.8
0.85	128	128	256	0.8	0.65	0.8
0.9	150	150	300	0.8	0.65	0.8

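### Randomisation is stratified by prior BTX status, but the primary non-inferiority test ignores the strata and no result by stratum is planned: a modest, conservative loss of precision and a reporting gap

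*Combined protocol and SAP*

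**What the plan says.** Section IV (Methodology) admits current BTX responders and excludes earlier failures: "If they had prior BTX and were clinical non-responders they will not be eligible". Allocation is equal ("they will be randomized (1:1) into the 3-injection site group") and uses prior status as a factor: "We plan on performing a stratified randomization so the number of BTX naïve and previous BTX responder patients will be equivalent in both arms". The stated reason for stratifying is to limit selection bias.

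Section VII (Primary Effectiveness) asks whether the overall 3-site success proportion is "non-inferior with a margin of 15% to that with BTX-10 at 3 months". Under Sample Size and Power Calculation: "The test statistic used is the one-sided Z test with a Type I error rate of 0.025". The design has "89 per group to achieve 80% power to detect a non-inferiority margin difference", with one reference rate for everyone: "The reference group (BTX-10) proportion is 0.85". Data analyses adds t-tests or chi-square tests, a completer analysis, an intent-to-treat analysis and four dropout scenarios.

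None of these uses prior BTX status. No stratum estimate, subgroup or interaction analysis is planned, and the expected share of naive patients is not given. In Section VI, the inclusion list names a previous BTX injection at least three months earlier; read literally, that leaves no naive patients.

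**The concern.** Two separate things are lost when a factor is used to randomise and then dropped from the analysis.

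The first is precision. Balancing the arms within strata removes between-stratum variation from the treatment difference. A simple two-sample Z test still counts that variation in its standard error, so its interval is wider than the design warrants.

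The second is visibility. The pooled difference is an average over two groups with different treatment histories: one selected because patients reported benefit from BTX, the other untested. Without a result by stratum, a reader cannot see whether the average describes both groups. A first-time patient is the obvious person to ask.

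**Working it through.** **Inputs from the documents.** Margin 0.15, one-sided alpha 0.025, 89 per arm, 1:1 allocation, success 0.85 in both arms under the alternative ("both BTX-10 and BTX-3 had the same response rate of 0.85").

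**Assumptions.** Stratum success rates, naive share and size of any naive-only deficit. The documents give none of these.

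**1. The plan's own figure.** With p = 0.85 in both arms, p(1−p) = 0.1275 and SE = √(2 × 0.1275/89) = 0.0535. Power = Φ(0.15/0.0535 − 1.96) = 80.0%. The stated 89 per arm reproduces.

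**2. Precision.** Take 10-site and 3-site success both at 0.95 in prior responders and 0.75 in naive patients, strata equal, so the overall rate is still 0.85.

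- Within-stratum variance: ½(0.95 × 0.05) + ½(0.75 × 0.25) = 0.1175.
- Variance used by the pooled test: 0.1275. The excess is the between-stratum part, 0.5 × 0.5 × 0.20² = 0.0100. The ratio 0.1175/0.1275 is 92%.
- True SE under stratified randomisation: √(2 × 0.1175/89) = 0.0514.
- Stratified power: Φ(0.15/0.0514 − 1.96) = 83.1%.
- Pooled power: Φ((0.15 − 1.96 × 0.0535)/0.0514) = 81.0%.
- Actual one-sided error of the pooled test: 1 − Φ(1.96 × 0.0535/0.0514) = 0.0206, below 0.025.

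Stratified power is 81.5% for rates 0.92/0.78 and 85.3% for 0.98/0.72. If both strata have 0.85, the variances coincide and the gain is near zero (80.4% against 80.1% in simulation).

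**3. A deficit in naive patients only.** Let f be the naive share, the naive deficit 0.20 and the prior-responder deficit 0, with 10-site success 0.85 in both strata. The pooled deficit is 0.20f. The chance of passing is Φ((0.15 − 0.20f)/SE − 1.96), where SE = √([0.85 × 0.15 + p₃(1 − p₃)]/89) and p₃ = 0.85 − 0.20f. For f = 0.20, p₃ = 0.81, SE = 0.0562 and the result is 49.9%. For f = 0.50 it is 13.1%. Simulation (200,000 trials per row, 89 per arm):

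| Naive share | Pooled deficit | Pooled test passes | Stratified test passes |
|---|---|---|---|
| 20% | 4 points | 49.9% | 51.6% |
| 30% | 6 points | 34.5% | 36.2% |
| 50% | 10 points | 13.5% | 14.5% |
| 70% | 14 points | 3.6% | 3.9% |
| 80% | 16 points | 1.7% | 1.8% |

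The stratified test passes slightly more often in every row. With 1:1 allocation inside each stratum, the stratum-size-weighted difference equals the pooled difference; only the standard error shrinks. With rates 0.75 naive and 0.95 prior, 50% naive and the same deficit, the figures are 11.5% pooled and 15.4% stratified.

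**4. What a stratum result can show.** With 44 naive patients per arm at 0.85, the 95% half-width is 1.96 × √(2 × 0.1275/44) = 0.149, about 15 points, and power for non-inferiority in naive patients alone is 50%.

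**The case against.** The strongest reply is that the plan answers the question it poses. The hypothesis in Primary Effectiveness concerns overall proportions. A pooled deficit of 4 or 5 points lies inside the 0.15 margin, so passing is then a correct decision for that hypothesis. The unstratified test is valid and errs on the safe side, the stated purpose of stratifying was balance between arms, and the gain in power is about 2 points. All of this stands, and it limits the point to efficiency and reporting.

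A reader might infer more, in three ways that the documents do not support.

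- *That the unstratified test is what hides a failure in naive patients.* It is not. Averaging with no stratum report hides it, and a stratified test averages in the same way.
- *That prior responders must pull the difference towards zero.* Section IV defines prior response by subjective improvement, not by the 50% reduction in the primary endpoint, so 0.95 is only an assumption. Equal efficacy of 3 sites in that group is part of what the trial tests. The reverse is arguable too: patients whom BTX helps under neither technique add no difference, and they would sit in the naive stratum.
- *That a claim for naive patients could rest on the naive-stratum estimate.* At this sample size it is too imprecise.

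What the reply does not answer is why a recorded randomisation factor appears nowhere in the analysis.

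**Conclusion.** The point holds as a mismatch between randomisation and analysis, with a modest consequence. Under assumed rates of 0.95 and 0.75 in equal strata, the planned test runs at about 0.021 instead of 0.025 and gives up about 2 points of power (81.0% against 83.1%). The loss vanishes as the stratum rates converge. It does not inflate type I error.

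The absence of any stratum result is a separate gap in what readers will be able to see. Its importance depends on the naive share: for a 20-point naive-only deficit, the chance of passing runs from about 50% at 20% naive to 4% or less at 70% or more. These figures describe assumed scenarios. They are not evidence that such a deficit exists, nor that the pooled test is wrong for the hypothesis stated.

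**What to change.** - **Primary test.** In Section VII (Sample Size and Power Calculation, and Data analyses), make the primary test a difference in proportions stratified by prior BTX status, using Mantel-Haenszel weights or a stratified Miettinen-Nurminen confidence interval. Keep the margin of 0.15, one-sided 0.025 and 178 patients. Use the same method in the completer, intent-to-treat and dropout-scenario analyses.
- **Stratum results.** Prespecify the month-3 difference with its 95% confidence interval in naive patients and in prior responders, with the numbers in each, labelled descriptive. Attach no separate non-inferiority claim to either stratum.
- **Adopt both together.** The stratified test alone would make a naive-only deficit slightly easier to miss.
- **Eligibility.** Reconcile the Section VI inclusion criterion on previous injection with the naive stratum in Section IV.

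The cost is a few lines of analysis text and one table. The factor is already needed for randomisation, so no new data are required. The change should be made before outcome data are seen; otherwise the stratum results would be post hoc.

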#### **Injection Procedure**

The injection procedure consists of injections of 100 U for IDO at 3 or 10 injection sites. The BTX will be reconstituted at a concentration of 10 U per 1 cc as is common practice. For example, a 100 U dose will be diluted with 10 cc of injectable saline. The diagram below shows the injection sites at the bladder base (just beyond the trigone). The procedure requires local lidocaine anesthesia only.

Figure 1. 3- and 10- site cystoscopic injection locations are outlined in the bladder.

Pre- and post-procedure antibiotics will be given at the discretion of the provider. After a negative urine analysis or if a patient has a positive dipstick (positive leukocyte esterase

and/or positive nitrites and/or positive blood) but is asymptomatic for a UTI, will proceed with Botox injections at the clinicians discretion. The patient's urethra will be prepped with betadine and 50 ml of 1% liquid lidocaine plain will be instilled, via catheter, into the patient's bladder and left for 10 minutes.

A flexible cystoscope will be used for the in-office procedure. This will be sterilized per standard office procedure between uses. A one-time use, Laborie injeTAK®, 23-gauge cystoscopic injection needle will be utilized as this is the needle used in both practices. The needle is retractable and can be adjusted to 0, 2, 3, 4, and 5 mm lengths. The needle will be extended out to 3 mm. Bladder wall thickness is dependent on the condition of the patient's bladder as well as degree of distention. Based on the literature, average bladder wall thickness on ultrasound of patients with OAB ranges from 4 to 6 mm. This can of course vary with degree of distention. Based on these findings, and in conjunction with previously mentioned MRI findings of nearly 20% extravasation using a 4 mm needle depth, we opted for a 3 mm needle depth.

Additionally, a recent meta-analysis showed no difference in efficacy or safety according to depth of injection (suburothelial vs. intradetrusor). Based on these findings, we will leave it up to the surgeon to decide between suburothelial or intradetrusor injections. This data, however, will be collected for analysis at the end of the study.

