#### Data analyses

A biostatistician will perform all statistical analyses using SAS or similar statistical software. Descriptive statistics will be calculated. A completer analysis will be conducted for those who finish the study per protocol. The primary endpoint will be assessed comparing incontinence episodes per day at 3 months after BTX injection. This comparison will also be made for all other visits using t-tests or chi-square tests, as appropriate.

Secondary endpoints will include adverse events and comparisons between 3-site and 10-site groups looking at the GRA responses between 3-site and 10-site groups at 3 months (± 14 days) post injection, 3-day voiding diary and OABq-SF and ICIQ-SF at 3 months (± 14 days) post-injection. We will also compare post-injection VAS scores to assess for tolerability, satisfaction, and pain. Changes from baseline will also be analyzed. This comparison will also be made for all other visits using appropriate statistical tests.

In addition to a completer analysis, we also plan on conducting an intent to treat analyses which will identify any subject not assessed at 3 months after the first BTX injection as a treatment failure. In order to assess for all possible situations, 4 different scenarios will be run: 1) All dropouts will be considered non-responders for both groups 2) All dropouts will be considered responders for both groups, 3) Dropouts in the BTX 10 group will be considered responders and those in the BTX 3 group, non-responders, and 4) Dropouts in the BTX 10 group will be considered non-responders while those in the BTX 3 group, responders.

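### UTI is compared between arms without a definition, a fixed culture trigger or allocation-blind classification, and no rule says which month-3 diary counts after a UTI

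*Combined protocol and SAP*

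**What the plan says.** **UTI as an outcome.** Section III states: "Our secondary aim is to assess whether less injection sites has fewer complications (UTI/ hematuria"). Section VII, Data analyses, adds: "Secondary endpoints will include adverse events and comparisons between 3-site and 10-site groups". The Injection Procedure text explains that the sham does not puncture the mucosa, partly so that UTI and hematuria rates can be compared.

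**How UTI is found.** For months 3 to 12, section IV says "OAB-q SF, GRA, ICIQ-SF, patient satisfaction, 3-day voiding diary, and UA will be collected", then "If necessary, a UCx will be ordered for evaluation". The two-week visit has the same arrangement, and the schedule table lists culture as needed. No section gives a symptom criterion, urinalysis threshold or culture result that makes an episode a UTI. The items listed for remote visits come by phone or mail and include no urine sample.

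**Who is blind.** "Patients will be blinded to the number of injections they will receive". The injecting provider performs the real and sham injections and so knows the arm. No blinded assessor is named.

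**What a UTI call does to the diary.** "If at any visit the patient is found to have a UTI, they will be prompted to repeat that visits questionnaires and 3-day diary", after UTI treatment is completed. Primary Effectiveness averages two consecutive 3-day diaries, while the schedule shows one 3-day diary entry per visit. Neither mentions a post-UTI diary.

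**The concern.** The UTI comparison depends on a judgement: whether to send a culture, and whether to call the episode a UTI. Background and Rationale expects that fewer sites may reduce UTI. Someone who knows the arm and shares that expectation could, without intending to, look less hard in the 3-site arm, and the plan has no safeguard against this.

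The judgement is harder than usual in this population. Entry requires at least 8 voids per day and the efficacy endpoint is urgency incontinence; that these overlap with UTI symptoms is a clinical inference, not a statement in the documents.

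A second gap follows from the same call. It decides who completes another month-3 diary, and without a rule the analyst could choose between diaries after seeing the data.

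**Working it through.** **1. The plan's own figure.** The inputs, from Sample Size and Power Calculation, are 0.85 in both arms, margin 0.15, one-sided 0.025 and 80% power.

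n per arm = (1.960 + 0.842)² × 2 × 0.85 × 0.15 / 0.15² = 88.95, so 89 per arm and 178 in total. The stated figure is reproduced. It covers the primary endpoint only; the UTI comparison simply inherits 89 per arm.

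**2. Unequal UTI detection with no true difference.** The only documented UTI rate is above 10% (Possible Risks of Injection Procedure). Assumptions: true rates of 15%, 20% and 30% in both arms; detection of 90% (10 sites) and 70% (3 sites); no false-positive calls. Observed rate = true rate × detection. The last column is the probability that a pooled two-sided 0.05 z-test finds fewer UTIs with 3 sites, by exact binomial enumeration at 89 per arm.

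| True rate | Observed, 10 sites | Observed, 3 sites | False finding |
|---|---|---|---|
| 15% | 0.15 × 0.90 = 13.5% | 0.15 × 0.70 = 10.5% | 8.8% |
| 20% | 18.0% | 14.0% | 10.6% |
| 30% | 27.0% | 21.0% | 15.0% |
| 15-30%, equal detection | same | same | 2.4-2.5% |

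The rate ratio is 0.70 / 0.90 = 0.78 throughout. At a 15% true rate the gap is 3 points, or 0.03 × 89 = 2.7 patients. If over-diagnosis also differs (assumed specificity 0.90 with 10 sites, 0.97 with 3), the false-finding probability is 34-36%. Swapping the detection rates produces the same error in the opposite direction.

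**3. Noise that is equal in both arms.** With perfect ascertainment, power to detect a halving from 15% to 7.5% is 35%. With sensitivity 0.8 and specificity 0.90-0.95 in both arms it is 15-19%.

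**4. The repeat diary and the primary test.** Assumptions: true rates at the null boundary (0.70 with 3 sites, 0.85 with 10 sites); the repeat diary replaces the first; half of the failures who repeat become successes. With a share u of an arm repeating, q = p + u × (1 − p) × 0.5. One-sided type I error ≈ Φ[(q3 − q10 + 0.15) / √((q3(1 − q3) + q10(1 − q10)) / 89) − 1.960]. The last column is exact enumeration.

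| Repeating, 3 sites | Repeating, 10 sites | q3 | q10 | Formula | Exact |
|---|---|---|---|---|---|
| 0% | 0% | 0.7000 | 0.8500 | 2.5% | 2.6% |
| 5% | 10% | 0.7075 | 0.8575 | 2.5% | 2.6% |
| 5% | 15% | 0.7075 | 0.8613 | 2.2% | 2.2% |
| 13.5% | 13.5% | 0.7203 | 0.8601 | 3.7% | 3.8% |
| 10.5% | 13.5% | 0.7158 | 0.8601 | 3.1% | 3.2% |

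The last two rows apply the 15% case from step 2 as if every UTI fell at month 3. Under-diagnosis in the 3-site arm lowers the error relative to equal detection (3.2% against 3.8%). The excess over 2.6% comes from replacing diaries at all, because the arm with more failures has more to convert. Inflation needs more repeats in the 3-site arm: by the formula, 10% against 5% gives 3.8%, and 15% against 5% gives 5.0%.

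**The case against.** The strongest reply is that detection does not rest on culture alone. Urinalysis is scheduled at all seven visits, adverse events are asked about at every follow-up, the patients who report them are blind, and section VIII routes adverse events to the research nurse before the principal investigator. Nothing says that the injector makes the UTI call or that follow-up clinicians know the arm. The detection rates above are assumed, the illustrated gap at a 15% rate is under 3 patients per arm, and UTI is an unpowered secondary comparison.

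This limits the size of the problem but does not close it. No urinalysis result is tied to a UTI diagnosis, remote visits list no urine, and the absence of a stated unblinded assessor is not a requirement for a blinded one.

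A reader might infer three stronger points, which the documents do not support:

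- **That the UTI call biases efficacy towards 3 sites.** Fewer UTI calls in that arm mean fewer repeat diaries there, so the second chance goes to the 10-site arm. Step 4 shows that this does not add to false non-inferiority.
- **That bacteriuria at injection tilts the UTI comparison.** A patient with a positive dipstick "but is asymptomatic for a UTI, will proceed with Botox injections at the clinicians discretion", so the allowance is confined to asymptomatic patients, and it also covers blood-only positives. Randomisation balances prior bacteriuria in expectation; miscounting it adds noise rather than favouring an arm.
- **That outcome assessors are unblinded.** The documents only fail to require that they be blind.

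**Conclusion.** The concern holds as two gaps in specification. First, UTI is a named secondary comparison with no definition, a discretionary culture and no blinding required beyond the patient, so arm-dependent detection cannot be excluded. Its size and direction cannot be derived from the documents; the 9-15% false-finding range rests entirely on the assumed 90% and 70% detection and true rates of 15-30%. Second, nothing says which month-3 diary enters the primary endpoint after a UTI. That leaves an analysis choice open, but it is not evidence of bias towards 3 sites. Both should be settled before outcome data are examined, because cultures that were never sent cannot be recovered at analysis. The primary sample size is unaffected.

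**What to change.** For outcome counting only:

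- **Trigger.** Send a culture on the follow-up urine already collected whenever leukocyte esterase or nitrites are positive or new urinary symptoms are reported, alike in both arms.
- **Definition.** Count a UTI endpoint only with a positive culture plus symptoms that are new or worse than a named reference, for example the pre-injection baseline. Without a named reference, OAB symptoms returning as the effect wears off could count as worse than at the last visit.
- **Classification.** Have existing staff who do not hold the allocation classify each event.
- **Separate reporting.** List clinically treated events without a positive culture, and events from remote visits without urine, on their own lines.
- **Baseline flag.** Record the Visit 2 dipstick result, and any culture that was taken, as a descriptive flag. No new pre-injection culture is asked for.
- **Diary rule.** Prespecify which month-3 diary is used after a UTI, for example the repeat diary, completed before any re-injection, for culture-confirmed UTI only. Add a sensitivity analysis using the first diary. State how the rule fits with the average of two diaries.

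The cost is a modest number of extra cultures, a short definition and fewer counted events, which reduces already low power for UTI. N stays at 178. Treatment, antibiotic and injection decisions stay as written.
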